Most of the data on SD in cancer patients come from patients with breast cancer, gynecologic neoplasms, and prostate cancer, most of whom receive hormonal cancer treatments and cytotoxic chemotherapy, and have often undergone mutilating cancer surgeries.

There are limited prospective studies carried out with heterogeneous collection instruments, which does not allow obtaining adequate and complete information on the real situation of the problem.

As a source of local data, there is a study to characterize sexual dysfunction in a cohort of cancer survivor patients derived from the European CLARIFY H2020 project (Cancer Long Survivor Artificial Intelligence Follow-Up) that we carried out at the Puerta de Hierro University Hospital from May 2020 to May 2022.

A total of 383 patients were included, distributed according to diagnosis in breast cancer 68.1% (261), lung cancer 26.3% (101) and lymphomas 5.48% (21).

Globally, 69% of men vs. 31% of women reported being sexually active and 76% of women vs. 24% of men had general sexual dissatisfaction.

In our study, the largest sample of patients was women with breast cancer (261), which corresponds to the highest overall frequency reported in the literature of this type of neoplasm.

In relation to the stage, patients with early breast cancer treated and followed up receiving hormonal therapy showed a greater tendency to suffer moderate disorders of the phases of sexual response, while patients with a diagnosis time greater than 5 years showed a tendency to not present alterations. Statistically significant associations were confirmed in patients with metastatic breast cancer to present severe disorders of the phases of sexual response.

Regarding the specific characteristics of patients with lung cancer, which represented a smaller sample size (101), 66.3% (67) were men, the median age was 64 and 61 years in men and women respectively. 45% of women and 41% of men reported being sexually active. The absolute frequency of overall sexual dissatisfaction was 8.8% in men vs. 2.8 in women.

Men showed a tendency to develop severe alterations in the phases of sexual response. On the other hand, a statistically significant association was evidenced for severe sexual response disorders in women. Of these, 35.2% received chemotherapy, 26.4% immunotherapy and 20.5% targeted therapies.

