Additionally, the knowledge obtained will allow to generate education about SD to the entire treating medical team and patients to overcome the barriers that prevent adequately addressing this condition.

7. General Objective

To identify and describe the type, frequency, and severity of SD in patients with lung cancer and to generate targeted clinical approach and oncological follow-up strategies based on specific findings in this population.

8. Secondary Objectives

- Describe the clinical, cultural, and sociodemographic characteristics of the study population.
- To characterize differences in sexual dysfunction in patients with lung cancer according to age, sociodemographic characteristics, region of residence, and type of cancer treatment.
- Identify risk factors for the development and severity of sexual dysfunction.
- To promote education and awareness among the health team on the identification and characteristics of sexual dysfunction in patients with lung cancer.
- To collect information to generate recommendations for the multidisciplinary approach and management of sexual dysfunction during oncological follow-up applicable to current oncology practice.
- To propose education strategies on the management of sexual dysfunction in patients with lung cancer aimed at patients and their families.
- To generate a collaborative network of Ibero-American research.

9. Methods and procedures envisaged, including statistical and other analytical tests

The recruitment will be carried out from July 2023 and will be carried out until December 2023, the analysis of the information will be carried out from January to March 2024.

Clinical and demographic variables (Annex 1) will be collected by the treating oncologists and recorded in an electronic data collection notebook designed for this study, which will be accessed through a personal username and password.

Data anonymization will be ensured for all patients. To this end, they will identify themselves with a numerical code in order to respect the confidentiality of personal data. The patient's initials and medical record number will be separated from the rest of the data and will not be included in the study database.

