Measurements of sexual function will be performed through an electronic survey that will be sent to patients who agree to participate in the study and sign the informed consent. This electronic survey will be hosted on an exclusive study platform, which the patient will enter through a user corresponding to the anonymization numerical code and a personal password assigned after signing the informed consent.

The survey will consist of single-choice questions based on two validated questionnaires to explore and diagnose sexual dysfunction in women (FSM) and men (FSH) separately, which have been evaluated and translated into Spanish by a local research group in the Valencian Community and are available for use in the primary care setting in Spain. These instruments were selected because of the possibility of self-administration, their history of efficacy in assessing complete sexual function in the general population, and their low level of complexity. Through this instrument, criteria of the phases of sexual response according to DSM V (FSH) and DSM IV (FSM) will be evaluated, as well as a descriptive parameter of sexual activity. (Appendices 2 and 3)

The information entered by patients will only be visible by the principal investigator, who will have a personal username and password to access the data.

10. Statistical analysis

A descriptive analysis of the variables will be carried out; for the characteristics a univariate analysis. The qualitative variables will be determined with absolute and relative frequencies and the quantitative variables by measures of central tendency and dispersion, with mean and standard deviation for those with normal and median distribution and interquartile range for those with non-normal distribution. Subsequently, an inferential analysis will be performed, with chi2 distribution to evaluate the correlations between the different variables and the main outcomes in the measurement of sexual function.

Possible trends in association between variables and outcomes will be evaluated and the main trends described will be carried out through a multivariate analysis.

Logistic regression analyses will be performed to determine risk factors

Statistical analyses will be carried out using the SPSS Statistics 20 or R program.

11. Full project overview in understandable language

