12.2 Criteria for the inclusion/exclusion of research participants

Inclusion criteria

- Age greater than or equal to 18 years and less than or equal to 70 years.
- Diagnosis of lung cancer stages IB to IV.
- Have received systemic cancer treatment for at least 3 months or be under cancer follow-up after having received systemic therapy for at least 3 months with stable tumor disease or in partial or complete response on imaging.
- ECOG ≤ 2

Exclusion Criteria

- Patients with comorbidities (kidney failure, cardiovascular diseases or similar) not controlled with corresponding medical management.
- Individuals with physical disability or cognitive impairment that prevents them from completing the electronic data collection form.

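### Does Section 10 need a written outcome definition and a rule for sexually inactive patients before its risk-factor models can be trusted?

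*Combined protocol and SAP*

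**What the plan says.** Section 8 sets this secondary objective: "Identify risk factors for the development and severity of sexual dysfunction". The analysis that serves it is described in three short statements in Section 10. Chi-square tests relate the variables to "the main outcomes in the measurement of sexual function"; "the main trends described will be carried out through a multivariate analysis"; and "Logistic regression analyses will be performed to determine risk factors". None of them names a dependent variable, a cut, or a choice between binary and ordinal regression.

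Section 9 describes the measurement. There are two validated, self-administered questionnaires, FSM for women and FSH for men. They apply DSM criteria to the phases of sexual response, "as well as a descriptive parameter of sexual activity", and Section 9 refers to Appendices 2 and 3 for them. Section 10 does not mention activity again.

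The inclusion criteria in Section 12.2 cover age ("Age greater than or equal to 18 years and less than or equal to 70 years"), stage, systemic treatment and performance status. No inclusion or exclusion criterion concerns sexual activity, so inactive patients can enrol. For the earlier lung cohort, Section 6 reports that "45% of women and 41% of men reported being sexually active".

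**The concern.** Section 8 names two targets, development and severity, and Section 10 answers with one sentence. The dependent variable could be any dysfunction, severe dysfunction, one phase, or an overall score. Patients without sexual activity could be counted as unaffected, counted as affected, or left out.

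In the sponsor's earlier lung cohort those patients were probably the majority, so the choice could matter. Frequency is part of the general objective and depends directly on the denominator. For risk factors, a characteristic such as age or treatment type might lower activity without altering function among active patients. It would then look protective, neutral or harmful according to the coding alone. If the coding or the severity cut were picked after seeing the data, the reported risk factors would partly reflect that pick.

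**Working it through.** The plan gives no sample size, power or expected frequency for this analysis, so there is no stated figure to reproduce. As an input check, 67/101 = 66.3%, which matches the share of men in Section 6.

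**Inactive share.** Inputs from Section 6: 101 lung patients, 67 men (so 34 women), 41% of men and 45% of women active. The two percentages sum to 86%, so they are read as shares within each sex.

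- Active: 0.41 × 67 + 0.45 × 34 = 27.5 + 15.3 = 42.8, and 42.8/101 = 42.4%.
- Inactive: 57.6% overall; 59% of men and 55% of women.
- No whole count fits exactly (27/67 = 40.3%, 28/67 = 41.8%; 15/34 = 44.1%, 16/34 = 47.1%), so some answers may have been missing. Nearby counts give 57 to 59 inactive patients. The Wilson 95% interval for 58/101 is 47.7% to 66.6%.

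**Frequency of dysfunction.** Let a = 0.424 be the active share and p the assumed frequency among active patients, for a score that only active patients can have. Counting inactive patients as unaffected gives a·p; leaving them out gives p; counting them as affected gives a·p + (1 − a).

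| Assumed p | Unaffected | Left out | Affected |
|---|---|---|---|
| 30% | 13% | 30% | 70% |
| 50% | 21% | 50% | 79% |
| 77% | 33% | 77% | 90% |

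The outer columns differ by 1 − a, hence 55 points in women and 59 in men. This is a maximum: any phase that can be scored without activity reduces it.

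**Odds ratios.** Assume a factor with no effect among active patients (p = 50% in both groups). With activity of 50% without the factor and 30% with it:

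- Inactive = unaffected: 25% against 15%, OR = (0.15/0.85)/(0.25/0.75) = 0.53.
- Inactive = affected: 75% against 85%, OR = (0.85/0.15)/(0.75/0.25) = 1.89.

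The same formulas give the other rows. The last column is the simulated share of two-sided 5% chi-square tests that reject, with 200 patients, 40% of them with the factor.

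| Activity without / with factor | Unaffected | Left out | Affected | Rejection |
|---|---|---|---|---|
| 50% / 30% | 0.53 | 1.00 | 1.89 | 40/5/40% |
| 46% / 36% | 0.73 | 1.00 | 1.36 | 13/5/14% |
| 45% / 41% | 0.89 | 1.00 | 1.13 | 6/5/6% |

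The first two gaps are assumed. The third borrows the size of the only lung-cohort activity contrast in the documents, which is between the sexes.

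The 40% is not an error rate of the plan. If inactivity is taken to be part of dysfunction, a factor that lowers activity really does have an odds ratio of 1.89, and 40% is power. The three codings estimate different quantities, so one null hypothesis cannot serve for all.

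With no effect on activity or on dysfunction, taking the smallest p-value over the three codings gives about 11% significant results, and about 18% if two severity cuts are also open. Nothing in the documents suggests such selection.

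**The case for a change.** The strongest case for a change is that complete scoring instructions in the appendices would still not say which result enters which model, or whether inactive patients are in the denominator. Section 9 cites the appendices for the questionnaires, and Section 10 does not refer to them for analysis. The effect need not be small: with activity of 50% against 30%, a true odds ratio of 2.0 among active patients (50% against 66.7% affected) becomes 0.75 or 3.0 under the extreme codings. The results are also meant to inform follow-up guidelines, and the remedy would cost only wording.

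The silence of Section 10 is real and that part stands. The step from silence to a required change does not. Section 6 reports the group's earlier results as moderate or severe disorders of the response phases, so a graded outcome per phase is the natural reading. Nor is there an obvious rule to impose. Restricting the models to patients with a computable score conditions on activity, which dysfunction may itself reduce. With the earlier sex mix, and 300 recruits assumed purely for illustration, it would leave about 300 × 34/101 × 0.45 = 45 women and 300 × 67/101 × 0.41 = 82 men. A binary cut and an ordinal model for severity are both defensible. Writing down one of these options would settle a debatable choice without correcting an error.

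**Conclusion.** No change follows; this is a gap that analysts can fill sensibly. In the available text, Section 10 leaves the dependent variable, the cut and the denominator unstated, but no rule that it does state is shown to give a wrong answer. The study is cross-sectional and mainly descriptive, uses validated instruments and records activity. An analyst can therefore take the scoring and grades from the questionnaires, report the inactive patients by sex, and give the denominator beside each result.

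The figure of about 58% inactive rests on reading the percentages within sex and on one small single-hospital cohort; a multi-country sample may differ. The 55- and 59-point differences are upper limits that apply only if no phase can be scored in inactive patients. The odds ratios depend on the assumed activity gap and lie close to 1 (0.89 and 1.13) for a gap of 45% against 41%.

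The conclusion assumes that Appendices 2 and 3, which could not be examined, contain usable scoring and some handling of inactive respondents. If they contain neither, the gap would be wider than judged here.

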12.1 Justification for the involvement of human beings in the research project

Due to the observational nature of the study, there is no possibility that the study will generate any type of risk in the subjects studied, since it does not imply any change in the patient's care with respect to their normal clinical follow-up. The research protocol will be submitted for approval by the research ethics committees (CEIC) of the participating institutions.

Prior to the commencement of the study, the protocol, clinical information questionnaire, patient information sheet, and informed consent for the study will also be submitted for approval by the Clinical Research Ethics Committee (CEIC).

Patients who meet all inclusion criteria and give informed consent will be recruited. Each subject invited to participate in the study will be given a written document called a "Patient Information Sheet" that will contain the relevant information necessary for them to decide if they want to participate in the study. The investigator will inform the patient as fully as possible of the details of the study. Participating subjects may withdraw their consent to the use of their data in the analysis at any time, without giving a reason and without incurring any liability or loss.

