12.4 Study modality: open, single-blind or double-blind

Analytical cross-sectional observational study.

12.5 Deadlines and details of information for potential research participants, including proposed methods for communicating such information.

Not applicable

12.6 Documentation, visual or other material to be used in the request for consent, or, in the case of persons unable to consent, for authorisation to participate in the research

1. Patient information sheet that will contain the relevant and necessary information for the patient to decide if they want to participate in the study. (Annex 4)
2. Informed consent (Annex 5), which each researcher must explain to the patient as completely as possible, specifying in understandable language the characteristics of the research project.

12.7 Provisions to ensure respect for the privacy of research participants and to ensure the confidentiality of personal data

The study will be conducted in accordance with the Good Clinical Practice (GCP) Standards.

The confidentiality of the data will be guaranteed in accordance with the provisions of Organic Law 3/2018, of 5 December, on the Protection of Personal Data and guarantee of digital rights and will separate personal clinical data in accordance with current legislation (Law 14/2007, of 3 July, on biomedical research).

All patients' data will be anonymized. To this end, the patient will be identified by means of a numerical code in order to respect the confidentiality of the patients' personal data. The patient's initials and medical record number will be separated from the rest of the data, not included in the study database.

Access to personal information will be restricted to the study investigators, the HUPHM clinical research ethics committee and specialized personnel authorized to verify the data and procedures of the study, always maintaining the confidentiality of the latter in accordance with current legislation.

The informed consent will be written in Spanish and in understandable language.

Subjects participating in the study may withdraw their consent to the use of their data in the analysis at any time, without giving a reason and without incurring any liability or loss.

12.8 Forecasts for the processing of information that may be generated during research and of relevance to the present or future health of participants and members of their families

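### The protocol does not say how eligible patients are selected for invitation and counts neither those left out nor those who decline, so selection behind the frequency of sexual dysfunction cannot be assessed

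*Combined protocol and SAP*

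**What the plan says.** Section 7 makes a frequency the general objective: "To identify and describe the type, frequency, and severity of SD in patients with lung cancer". Section 12.4 gives the design as "Analytical cross-sectional observational study".

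Section 12.1 holds the recruitment rule: "Patients who meet all inclusion criteria and give informed consent will be recruited". It goes on, "Each subject invited to participate in the study will be given a written document", so there is an invitation step, but nothing says which eligible patients are invited or whether invitations are recorded. Section 12.5, whose heading covers information for potential participants and how it is communicated, is marked not applicable.

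Section 9 gives the period: "The recruitment will be carried out from July 2023 and will be carried out until December 2023". It also says that SD is measured by an "electronic survey that will be sent to patients who agree to participate in the study and sign the informed consent". The treating oncologists record the clinical and demographic variables. No data are planned on patients who do not enrol.

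Section 10 plans absolute and relative frequencies, chi-square tests, a multivariate analysis and logistic regression. It mentions no participation rate, no comparison of participants with non-participants, no weighting and no sensitivity analysis. No sample size or expected participation is stated anywhere in the text supplied.

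**The concern.** A frequency needs a denominator. Entry to a survey on sexual function may plausibly depend on sexual function itself, or on age, sex or culture. If it does, the observed frequency is shifted by an amount that a larger sample does not reduce.

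Two aims are exposed. One is the overall frequency. The other is the comparison by region of residence and treatment in section 8: if sites differ in whom they invite or in who accepts, that difference is mixed with any real difference in SD.

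The information is also lost for good. Loss after consent can be examined later, because consenting patients have a code and oncologist-recorded clinical data. Patients who were never invited, or who declined, leave no planned record, so nothing can be reconstructed at the analysis.

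**Working it through.** The plan states no sample size, precision or participation rate, so there is no figure of its own to reproduce. The check has two parts: a reading of the text, and two illustrations of size.

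**Reading.** Sections 9, 10 and 12 are where a sampling rule, an invitation log, a refusal count or a participation rate would normally stand. None contains one. Section 12.2 (eligibility) and section 9 (recruitment window) do define a target population. What is missing is its enumeration and the fraction that enters.

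**Illustration 1: selection related to SD.** Let p be the true frequency and k the ratio of the chance of entering (being invited and accepting) for patients with SD to that for patients without. Both are assumptions; 60% and 1.5 are not in the documents.

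Observed frequency = pk / (pk + 1 − p)

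- p = 0.60, k = 1.5: 0.90 / (0.90 + 0.40) = 0.692
- p = 0.60, k = 1/1.5: 0.40 / (0.40 + 0.40) = 0.500
- p = 0.77, k = 1.5: 1.155 / (1.155 + 0.23) = 0.834
- p = 0.77, k = 1/1.5: 0.513 / (0.513 + 0.23) = 0.691
- k = 1: observed = p, no bias

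The 77% comes from a 2022 study cited in section 6. It is moderate to severe SD in women with lung cancer, so it serves here as a second value of p and not as an expected result for this study.

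For scale, the 95% half-width at an assumed n = 200 and p = 0.60 is 1.96 × √(0.60 × 0.40 / 200) = 0.068, about 7 points. This shrinks as n grows; the shifts above do not.

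**Illustration 2: what an unknown participation fraction costs.** Let q be the frequency observed in participants and f the share of eligible patients who take part. With no assumption about non-participants, the true frequency among all eligible patients lies between qf and qf + (1 − f), a width of 1 − f. With q = 0.77 and f assumed:

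- f = 0.9: 69.3% to 79.3%
- f = 0.7: 53.9% to 83.9%
- f = 0.5: 38.5% to 88.5%
- f = 0.3: 23.1% to 93.1%

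If non-participants differ from participants by only 20 points either way (also an assumption), the true frequency is q ± 0.20 × (1 − f): 75% to 79% at f = 0.9, 71% to 83% at f = 0.7, 67% to 87% at f = 0.5 and 63% to 91% at f = 0.3.

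The interval that applies depends on f. Under the plan as written f will not be known, so a reader could not choose among these rows.

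**The case against.** The strongest reply is that the recruitment sentence can be read as covering every eligible patient who consents, and that no section gives sites discretion over whom to invite. This stands as far as it goes. A reader might infer that investigators are free to hand-pick patients, but the text does not say so; it is silent. The silence is still the problem, because the sentence governs entry after eligibility and consent, and the step before it has no rule and no record.

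A reader might also infer that the treating oncologists will avoid raising the subject, since section 6 speaks of education to "overcome the barriers that prevent adequately addressing this condition". The documents do not support this. The barriers are unspecified, the education is aimed at the treating team and patients alike, and the subject is handling SD in care, not handing over a study information sheet. The answers go to an electronic platform and are visible only to the principal investigator. The concern does not need this inference.

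It would likewise be too strong to say that the study has no known source population. The eligibility criteria and the recruitment dates define one; it is just not counted.

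Three further points stand. The sizes shown are hypothetical and do not show that bias is likely. Standardising to a few recorded variables cannot correct selection on SD within those strata. A tally of people who did not consent needs ethics and data-protection review, and small cells at a site could be identifying.

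Finally, the opening part of the document and the annexes were not available, so a log there cannot be ruled out. The sections where such a rule belongs are available and silent.

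**Conclusion.** The point holds in this form: the method of selecting patients for invitation is not specified, and participation is not counted. The reported SD frequency will therefore rest on an unknown fraction of the eligible patients, and selection at the invitation and consent stage can be neither assessed nor bounded.

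The possible size is material. A true 60% would appear as 69% or 50% under an assumed 1.5-fold selection in either direction, shifts of 9 and 10 points against about 7 points of sampling error at an assumed 200 patients. That comparison rests entirely on the assumed frequency, ratio and sample size. It shows what could go undetected, not what will happen.

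The study can run without the change. Since the missing counts cannot be recovered afterwards and the remedy is cheap, it should be made.

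**What to change.** In section 12.1, require each site to invite consecutively all eligible patients seen in the recruiting clinics during the July to December 2023 window. Require an identifier-free tally of patients eligible, not invited, declined and consented, by a few coarse variables: sex, age band, stage and treatment class. Make this subject to ethics approval, with categories broad enough that small site cells do not identify anyone.

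In section 10, add three items:

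- the participation rate, overall and by site or country;
- a comparison of participants with the eligible tally on the tallied variables;
- SD frequencies standardised to the tally as a sensitivity analysis, with a statement that this corrects only for the tallied variables and not for selection on SD itself.

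With the participation fraction known, worst-case bounds of the kind shown above can also be given.

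The cost is a small workload at each site, ethics review of the tally in the participating countries, and a participation rate that may look low. Patients undergo no added procedure.
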